2.4.6.2 Pharmacodynamics/genomics analyses

All biomarkers listed in [Section 2.1.6](#) will be summarized in the Exposed population defined as patients who actually received at least 1 dose or part of a dose of the IMP. Baseline values will be the last value collected prior to the first IMP. For randomized but not treated patients, baseline value will be the last value collected prior to the randomization. Descriptive statistics (including number, mean, SD, median, Q1, Q3, min, max) of biomarkers at baseline will be summarized.

For all parameters including antigen-specific IgEs with a positive (≥ 0.35 IU/mL) incidence of greater than 25% at baseline, values at each visit, absolute change from baseline and percent changes from baseline will be summarized in descriptive statistics by treatment group and time point. Values reported as below the LLQ (lower limit of quantitation) will be imputed as a value one half of the LLQ.

Number and percentage of patients with no positive (≥ 0.35 IU/mL) antigen-specific IgE result, with positive (≥ 0.35 IU/mL) result for only one antigen, and with positive (≥ 0.35 IU/mL) results for at least two antigens will be summarized by treatment group and time point. Same analysis will also be performed using LLQ as the threshold.

Summary plots (mean +/- standard error of the mean) on values at each visit, absolute changes from baseline and percent changes from baseline will be provided for each biomarker by treatment group.

Exploratory analysis of DNA/RNA will be addressed in a separate document.

2.4.7 Analyses of vaccine response

For patients who receive vaccination, vaccine IgG in serum prior and after vaccination will be summarized by treatment groups with descriptive statistics.

2.4.8 Analyses of health economics variables

Analyses of health care resource utilization will be performed under the responsibility of the Health Economics and Reimbursement Argumentation department of Sanofi. Methods and results will be made available in a separate report.

2.5 DATA HANDLING CONVENTIONS

2.5.1 General conventions

The following formulas will be used for computation of parameters.

Demographic formulas

Age is calculated as:

$$\text{Integer part of (informed consent date - birth date)/365.25}$$

Age of onset of asthma is calculated as:

$$\text{Integer part of (asthma onset date - birth date)/365.25}$$

Time since first diagnosis of asthma (years) is calculated as:

$$\text{(Year of randomization - Year of first diagnosis of asthma) + (month of randomization - month of first diagnosis of asthma)/12}$$

Time since cessation of smoking is calculated as:

$$\text{(Year of randomization - Year of cessation) × 12 + (month of randomization - month of cessation)}$$

Time since last asthma exacerbation (months) is calculated as:

$$\text{(Year of randomization - Year of last asthma exacerbation) × 12 + (month of randomization - month of last asthma exacerbation)}$$

BMI is calculated as:

$$\text{Weight in kg / (height}^2 \text{ in meters)}$$

Smoking quantity (pack-year) is calculated as following:

$$\text{Number of pack-year} = \text{(packs smoked per day) × (years as a smoker)}$$

Renal function formulas

For patients ≥ 18 years old, creatinine clearance (CLcr) value will be derived using the equation of Cockcroft and Gault:

$$\text{CLcr (ml/min)} = \text{(140 - age) × weight (kg) × (1 - 0.15 × sex (0-M, 1-F)) / (0.814 × creatinine (}\mu\text{mol/l))}$$

CLcr will be calculated using the last weight measurement on or before the visit of the creatinine measurement and age at the lab sampling date. Here age is calculated as following:

$$\text{Age} = \text{integer part of } (\text{lab sampling date} - \text{birth date}) / 365.25$$

For patients < 18 years old, CLcr value will be derived using the equation of GFR Bedside Schwartz

$$\text{GFR (mL/min/1.73 m}^2\text{)} = k \times \text{height (cm)} / \text{sCr (mg/dL)} ,$$

Where the coefficient k=0.65 for adolescent male patients, or k=0.55 for adolescent female patients.

2.5.2 Data handling conventions for secondary efficacy variables

Calculation of salbutamol/albuterol or levosalbutamol/levalbuterol inhalations/day

A diary day is defined as the period beginning with an Evening diary, and ending with the following day's Morning Diary. The number of salbutamol/albuterol or levosalbutamol/levalbuterol inhalations per day is the sum of number of inhalations recorded in one diary day including the evening diary and the following day's morning diary.

Periodical average of daily efficacy endpoints at designated study days

For the daily efficacy endpoints, the time period used to calculate the periodical average at each designated study day is summarized in [Table 7](#). Randomization day is used as the reference day (Day 1).

Table 7 - Periodical average of daily efficacy assessment

Time point	Morning PEF, asthma symptom score, number of awakenings	Evening PEF, asthma symptom score	Number of inhalations/day of salbutamol/albuterol or levosalbutamol/levalbuterol for symptom relief
Day 15	2-15	1-14	Diary day 1-14
Day 29	16-29	15-28	Diary day 15-28
Day 43	30-43	29-42	Diary day 29-42
Day 57	44-57	43-56	Diary day 43-56
Day 71	58-71	57-70	Diary day 57-70
Day 85	72-85	71-84	Diary day 71-84
Day 113	86-113	85-112	Diary day 85-112
Day 141	114-141	113-140	Diary day 113-140
Day 169	142-169	141-168	Diary day 141-168

Time point	Morning PEF, asthma symptom score, number of awakenings	Evening PEF, asthma symptom score	Number of inhalations/day of salbutamol/albuterol or levosalbutamol/levalbuterol for symptom relief
Day 197	170-197	169-196	Diary day 169-196
Day 225	198-225	197-224	Diary day 197-224
Day 253	226-253	225-252	Diary day 225-252
Day 281	254-281	253-280	Diary day 253-280
Day 309	282-309	281-308	Diary day 281-308
Day 337	310-337	309-336	Diary day 309-336
Day 365	338-365	337-364	Diary day 337-364
Day 393	366-393	365-392	Diary day 365-392
Day 421	394-421	393-420	Diary day 393-420
Day 449	422-449	421-448	Diary day 421-448

Note: A diary day is defined as the period beginning with an Evening diary, and ending with the following day's Morning Diary. For example, diary day 14 includes the evening diary on day 14 and the morning diary on day 15.

2.5.3 Missing data

For categorical variables, patients with missing data are not included in calculations of percentages unless otherwise specified. When relevant, the number of patients with missing data is presented.

Handling of missing answer to the 7th question in ACQ-7

If the score is missing from the site report, the FEV1 % predicted value from spirometry test will be used to derive the 7th score. Only the spirometry performed on the same day when ACQ-7 is evaluated will be used. And if there are multiple FEV1% predicted values available on the same day, the lowest one will be used to score the 7th item. If the score of the 7th question is still missing but the questionnaire is complete at the prior visit, the missing score for the 7th question will be imputed as: (score of the 7th question at the prior visit) \times (sum of scores of the first six questions at the current visit) / (sum of scores of the first six questions at the prior visit). If the questionnaire from the prior visit is not complete either or if the ACQ-7 score at the prior visit is 0, which makes it infeasible to implement the algorithm, the missing score will be imputed as the average of the other six questions at the current visit. If scores of the first six questions are missing, then the ACQ-7 score for the current visit will be missing.

Handling of computation of treatment duration if investigational medicinal product end of treatment date is missing

For the calculation of the treatment duration, the date of the last dose of IMP is equal to the date of last administration reported on the Investigational Product Administration report form page. If this date is missing, the exposure duration should be left as missing.

The last dose injection should be clearly identified in the case report form and should not be approximated by the last returned package date.

Handling of medication missing/partial dates

No imputation of medication start/end dates or times will be performed. If a medication date or time is missing or partially missing and it cannot be determined whether it was taken prior or concomitantly, it will be considered a prior and concomitant medication.

Handling of adverse events with missing or partial date/time of onset

Missing or partial adverse event onset dates and times will be imputed so that if the partial adverse event onset date/time information does not indicate that the adverse event started prior to treatment or after the treatment-emergent adverse event period, the adverse event will be classified as treatment-emergent. No imputation of adverse event end dates/times will be performed. These data imputations are for categorization purpose only and will not be used in listings. No imputation is planned for date/time of adverse event resolution.

Handling of adverse events when date and time of first investigational medicinal product administration is missing

When the date and time of the first IMP administration is missing, all adverse events that occurred on or after the day of randomization should be considered as treatment-emergent adverse events. The exposure duration should be kept as missing.

The last dose injection should be clearly identified in the case report form and should not be approximated by the last returned package date.

Handling of missing assessment of relationship of adverse events to investigational medicinal product

If the assessment of the relationship to IMP is missing, then the relationship to IMP has to be assumed and the adverse event considered as such in the frequency tables of possibly related adverse events, but no imputation should be done at the data level.

Handling of missing severity of adverse events

If the severity is missing for 1 of the treatment-emergent occurrences of an adverse event, the maximal severity on the remaining occurrences will be considered. If the severity is missing for all the occurrences, a “missing” category will be added in the summary table.

Handling of potentially clinically significant abnormalities

If a patient has a missing baseline he will be grouped in the category “normal/missing at baseline.”

For PCSAs with 2 conditions, one based on a change from baseline value or a normal range and the other on a threshold value, with the first condition being missing, the PCSA will be based only on the second condition.

For a PCSA defined on a threshold and/or a normal range, this PCSA will be derived using this threshold if the normal range is missing; eg, for eosinophils the PCSA is >0.5 GIGA/L or $>ULN$ if $ULN \geq 0.5$ GIGA/L. When ULN is missing, the value 0.5 should be used.

Measurements flagged as invalid by the laboratory will not be summarized or taken into account in the computation of PCSA values.

2.5.4 Windows for time points

For the safety assessment, the reference date for the derivation of relative days of events or findings will be the date of first IMP administration. Selected safety variables will be summarized by the analysis window define in [Table 8](#) for the by visit descriptive analysis. All available values from central lab will be assigned to the appropriate visit window. In the event of multiple measurements of the same test in the same window, the one closest to the targeted visit date will be used for the by-visit summary. If they are at the same distance to the target day, the latest one will be used. For procedures planned on Visit 2, if it is done on the same date as the first IMP injection but the performance time is missing, it will belong to Visit 2 time window.

Table 8 – Time window for safety endpoints

Visit	Target Day	Time windows for							
		Vital signs	ECG endpoints	Clinical lab testing	Serum Pregnancy test	Urine Pregnancy test	Urinalysis, Serum immunoglobulins	Hepatitis B viral load	Hepatitis screen, HIV screen, ANA and Anti-ds DNA antibody
Visit 1 (Week -4±1)	-28±7	<-14	1-	<-14	1-		1-		1-
Visit 2 (Week 0)	1	-14-1-		-14-1-		1-		1-	
Visit 3 (Week 2)	15	1+-21	1+-21						
Visit 4 (Week 4)	29	22-35	22-56	1+-42		1+-42			
Visit 5 (Week 6)	43	36-49							
Visit 6 (Week 8)	57	50-63		43-70		43-70			
Visit 7 (Week 10)	71	64-77							
Visit 8 (Week 12)	85	78-98	57-126	71-98		71-98	1-126	1-126	
Visit 9 (Week 16)	113	99-126		99-126		99-126			

Visit	Target Day	Time windows for							Hepatitis B viral load	Hepatitis screen, HIV screen, ANA and Anti-ds DNA antibody
		Vital signs	ECG endpoints	Clinical lab testing	Serum Pregnancy test	Urine Pregnancy test	Urinalysis, Serum immunoglobulins			
Visit 10 (Week 20)	141	127-154		127-154		127-154				
Visit 11 (Week 24)	169	155-182	127-210	155-182		155-182	127-210	127-210		
Visit 12 (Week 28)	197	183-210		183-210		183-210				
Visit 13 (Week 32)	225	211-238		211-238		211-238				
Visit 14 (Week 36)	253	239-266	211-308	239-266		239-266	211-308	211-308		
Visit 15 (Week 40)	281	267-294		267-294		267-294				
Visit 16 (Week 44)	309	295-322		295-322		295-322				
Visit 17 (Week 48)	337	323-350		323-350		323-350				1+

Visit	Target Day	Time windows for							
		Vital signs	ECG endpoints	Clinical lab testing	Serum Pregnancy test	Urine Pregnancy test	Urinalysis, Serum immunoglobulins	Hepatitis B viral load	Hepatitis screen, HIV screen, ANA and Anti-ds DNA antibody
Visit 18 (Week 52)	365	351-378	309-406	351-378		351-406	309-406	>308	
Visit 19 (Week 56)	393	379-406		379-406					
Visit 20 (Week 60)	421	407-434		407-434					
Visit 21 (Week 64)	449	>434	>406	>434		>406	>406		

1-: up to 1st dose date/time; 1+: after 1st dose date/time;

For the efficacy assessment, the reference date for the derivation of relative days of events or findings will be the randomization day. If a patient receives IMP prior to the randomization by mistake, the reference date of efficacy assessment will be the date of the first IMP administration for that patient. For the primary analyses, all available values of scheduled measurements will be assigned to the appropriate visit window according to Table 9. In the event of multiple measurements of the same test in the same window, the one closest to the targeted visit date will be used for the by-visit summary. If they are at the same distance to the target day, the latest one will be used. For the on-treatment sensitivity analyses, only scheduled measurements collected during the treatment epoch will be assigned to a time window.

Table 9 – Time window for efficacy variables

Visit	Target Day	Time windows for		
		Pre-bronchodilator Spirometry, ACQ-5, ACQ-7	Post-bronchodilator spirometry, reversibility	AQLQ(S), EQ-5D-5L, HADS, SNOT-22, RQLQ(S)+12
Visit 1 (Week -4±1)	-28±7	<-14		
Visit 2 (Week 0)	1	-14-1 ¹	1 ¹	1 ¹
Visit 3 (Week 2)	15	1 ⁺ -21	1 ⁺ -21	
Visit 4 (Week 4)	29	22-35	22-42	
Visit 5 (Week 6)	43	36-49		
Visit 6 (Week 8)	57	50-63	43-70	
Visit 7 (Week 10)	71	64-77		
Visit 8 (Week 12)	85	78-98	71-126	1-126
Visit 9 (Week 16)	113	99-126		
Visit 10 (Week 20)	141	127-154		
Visit 11 (Week 24)	169	155-182	127-210	127-210
Visit 12 (Week 28)	197	183-210		
Visit 13 (Week 32)	225	211-238		
Visit 14 (Week 36)	253	239-266	211-308	211-308
Visit 15 (Week 40)	281	267-294		
Visit 16 (Week 44)	309	295-322		
Visit 17 (Week 48)	337	323-350		
Visit 18 (Week 52)	365	351-378	309-406	309-406
Visit 19 (Week 56)	393	379-406		
Visit 20 (Week 60)	421	407-434		
Visit 21 (Week 64)	449	>434	>406	>406

1⁻: up to randomization and before 1st dose date/time; 1⁺: after randomization or 1st dose date/time

For the pharmacokinetics/pharmacodynamics variables summary, the reference date for the derivation of relative days of measurements will be the date of first IMP administration if the patient is treated with study treatment, or the randomization date if the patient is not treated. Pharmacokinetics /pharmacodynamics variables will be summarized by the analysis window defined in Table 10 for the by visit descriptive analyses. All available values of measurements will be assigned to the appropriate visit window. In the event of multiple measurements of the same test in the same window, the one closest to the targeted visit date will be used for the by-visit summary. If they are at the same distance to the target day, the latest one will be used. For procedures planned on Visit 2, if it is done on the same date as the first IMP injection but the performance time is missing, it will belong to Visit 2 time window.

Table 10 – Time window for pharmacokinetics/pharmacodynamics variables

Visit	Target day	Time windows for					
		Eotaxin-3, ECP, total IgE, TARC	Exhaled NO	Systemic drug concentration	Anti-drug antibodies	Antigen-specific IgE	Periostin
Visit 1 (Week -4±1)	-28±7		<-14				
Visit 2 (Week 0)	1	1-	-14-1-	1-	1-	1-	1-
Visit 3 (Week 2)	15		1+-21	1+-21			
Visit 4 (Week 4)	29		22-56	22-42			1+-56
Visit 5 (Week 6)	43						
Visit 6 (Week 8)	57			43-70			
Visit 7 (Week 10)	71						
Visit 8 (Week 12)	85	1+-126	57-98	71-98	1-126	1-126	57-224
Visit 9 (Week 16)	113		99-126	99-140			
Visit 10 (Week 20)	141		127-154				
Visit 11 (Week 24)	169	127-210	155-210	141-210	127-266	127-266	
Visit 12 (Week 28)	197						
Visit 13 (Week 32)	225						
Visit 14 (Week 36)	253	211-308	211-294	211-308			
Visit 15 (Week 40)	281						
Visit 16 (Week 44)	309						
Visit 17 (Week 48)	337		295-350				
Visit 18 (Week 52)	365	>308	351-378	309-378	267-406	>267	>224
Visit 19 (Week 56)	393		379-406	379-406			
Visit 20 (Week 60)	421		407-434	407-434			
Visit 21 (Week 64)	449		>434	>434	>406		

Visit	Target day	Time windows for					
		Eotaxin-3, ECP, total IgE, TARC	Exhaled NO	Systemic drug concentration	Anti-drug antibodies	Antigen-specific IgE	Periostin
1-: up to 1 st dose date/time or randomization if patient is not treated; 1+: after 1 st dose date/time or randomization date if patient is not treated;							

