### 1.3 STUDY FLOW CHART FOR PATIENTS AFTER EARLY PERMANENT TREATMENT DISCONTINUATION

VISIT	ETD a																															E O S		
Week a		4	6	8	10	12	14	16	18	20	22	24	26	28	30	32	34	36	38	40	42	44	46	48	50	52	64							
Visit a		4	5	6	7	8		9		10		11		12		13		14		15		16		17		18	21							
Post-bronchodilator FEV 1	x	x		x		x					x						x									x	x							
Spirometry b	x	x	x	x	x	x		x		x		x		x		x		x		x		x		x		x	x							
Prior & concomitant medication	x	x	x	x	x	x		x		x		x		x		x		x		x		x		x		x	x							
Physical Examination	x										x																x							
Call IVRS/IWRS	x																														x			
Dispense or download e-diary/PEF meter c	x																																	
Dispense/Review Home Dosing Diary	x																																	
ACQ-7 d	x	x	x	x	x	x		x		x		x		x		x		x		x		x		x		x	x							
AQLQ(S)	x					x						x						x									x	X						
Health Care Resource Utilization	x																																	
Exhaled NO e	x																																	
Vital Signs f	x	x	x	x	x	x		x		x		x		x		x		x		x		x		x		x	x							
ECG	x	x				x						x						x										x						
Urine Pregnancy dipstick test	x																																	
Clinical lab testing g	x					x						x						x										X						
Hepatitis B viral load h	x					x						x						x										x						
AE/SAE recording	x	x	x	x	x	x		x		x		x		x		x		x		x		x		x		x	x							

VISIT	ETD a																																				E																	
		4	6	8	10	12	14	16	18	20	22	24	26	28	30	32	34	36	38	40	42	44	46	48	50	52	64	O																										
Week a																												S																										
Visit a		4	5	6	7	8		9		10		11		12		13		14		15		16		17		18	21																											
Urinalysis i	x																																																					
Serum immunoglobulins (IgG, IgM, IgA)	x																																																					
Systemic drug concentration (functional dupilumab) j	x	x		x		x		x				x						x																										x	x									
Anti-drug antibodies j	x					x						x																																	x	x								
Biomarker set k	x																																																					
Periostin	x																																																					
Antigen-specific IgE	x																																																					

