Archival serum l	x																																																					
EQ-5D-5L	x																																																					
HADS m	x																																																					
SNOT-22 n	x																																																					
RQLQ(S) +12 o	x																																																					
Vaccine IgG p	x																																																					

- a** Patients who permanently discontinue treatment early will continue the remaining visits per protocol schedule with a +/-5 day window until end of study. At the time of permanent treatment discontinuation, patients will perform early treatment discontinuation (ETD) visit with all the assessments defined for Visit 18 (EOT). Visit 19 (Week 56) and Visit 20 (Week 60) will not be performed.
- b** Forced expiratory volume (FEV1), PEF, Forced vital capacity (FVC), Forced expiratory flow between 25% to 75% of vital capacity (FEF25%-75%) at all visits; pulmonary function tests should be performed in the morning if possible, but if it could only be done at a different time of the day, the spirometry should be done at approximately the same time of the day at each visit throughout the study. Spirometry will be performed after a wash out period of bronchodilators according to their action duration, for example, withholding the last dose of salbutamol/albuterol or levosalbutamol/levalbuterol for at least 6 hours and withholding the last dose of LABA for at least 12 hours (ultra-long acting LABA like vilanterol should be withheld for at least 24 hours) and withholding the last dose of Long-Acting Muscarinic Antagonist (LAMA) for at least 24 hrs. This will be verified before performing the measurements.
- c** Electronic diary/PEF meter is used for daily recording of salbutamol/albuterol or levosalbutamol/levalbuterol use, asthma controller drug use, oral steroid requirements, nocturnal awakenings due to asthma symptoms, morning and evening asthma symptom NRS scores and AM and PM PEF. This device is dispensed at Visit 1 and information is downloaded from this device on the other indicated days.

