#### **11.4.4 Analyses of systemic drug concentration, anti-drug antibodies and pharmacodynamic variables**

##### ***11.4.4.1 Drug concentration analysis***

Concentrations of functional dupilumab in serum will be summarized using arithmetic and geometric means, SD, standard error of the mean (SEM), coefficient of variation (CV%), minimum, median, and maximum by treatment per visit.

Concentrations of functional dupilumab in serum will be used for population PK analysis by non-linear mixed effects modeling if warranted. Additional details of the analysis plan and the results will be provided in a separate document.

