2.1.5 Pharmacokinetic variables

Predose serum dupilumab concentrations at Visit 2 (Day 1), dupilumab trough levels at Week 2, Week 4, Week 8, Week 12, Week 16, Week 24, Week 36, Week 52 and follow-up serum dupilumab at Week 56, Week 60, Week 64 will be provided.

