2.3.3 Population for pharmacokinetics/pharmacodynamics analyses

The **PK population** will consist of all patients in the safety population with at least one evaluable serum concentration data. Patients will be analyzed according to the treatment actually received.

ADA population will consist of all patients in the safety population who had at least one reportable ADA results (either ‘ADA negative’ or ‘ADA positive’) after first dose of the study treatment.

Biomarkers will be analyzed in the **exposed population**, consisting of patients in the safety population.

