2.4.6 Analyses of pharmacokinetic and pharmacodynamics variables

2.4.6.1 Pharmacokinetic analyses

2.4.6.1.1 Analyses of serum concentrations of SAR231893 (REGN668)

Serum concentrations of SAR231893 (REGN668) will be summarized in the PK population using arithmetic and geometric means, SD, standard error of the mean (SEM), coefficient of variation (CV), minimum, median and maximum per sampling time. If date and/or time of the drug injection and/or sampling is missing then the concentration will not be taken into account. For drug-treated patients, where concentration values are below the lower limit of quantification (LLOQ), one-half of the LLOQ will be used. Values will be expressed in the tables with no more than three significant figures. For patients in the placebo group, concentration values are below the LLOQ will be taken into account with a plasma concentration considered equal to 0.

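### The by-dose dupilumab trough summaries from about Week 4 to Week 52 include samples taken after permanent discontinuation and are biased low, the geometric mean most of all

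*SAP*

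**What the plan says.** SAP 2.1.5 lists "dupilumab trough levels at Week 2, Week 4, Week 8, Week 12, Week 16, Week 24, Week 36, Week 52" and names Weeks 56, 60 and 64 separately as follow-up concentrations. In flow chart 1.2 of the protocol, the footnote on these samples requires them to be drawn before dosing.

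For patients who stop the drug, protocol 1.3 says "Patients who permanently discontinue treatment early will continue the remaining visits per protocol schedule with a +/-5 day window until end of study". The row "Systemic drug concentration (functional dupilumab") in that chart, read by column position, marks the early discontinuation visit and Weeks 4, 8, 12, 16, 24, 36, 52 and 64. Visits 19 and 20 (Weeks 56 and 60) are not performed in these patients.

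SAP 2.3.3 defines the PK population as "all patients in the safety population with at least one evaluable serum concentration data". SAP 2.4.6.1.1 states that concentrations "will be summarized in the PK population using arithmetic and geometric means", along with the SD, SEM, CV, minimum, median and maximum; protocol 11.4.4.1 groups them "by treatment per visit". For dupilumab patients, "where concentration values are below the lower limit of quantification (LLOQ), one-half of the LLOQ will be used". SAP 2.5.4 assigns samples to windows by the rule "All available values of measurements will be assigned to the appropriate visit window". The only sample-level exclusion in 2.4.6.1.1 is a missing date or time of injection or sampling.

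**The concern.** A trough describes exposure at the end of a dosing interval in a patient who is being dosed. A sample drawn months after the last injection is a washout value, yet nothing in the SAP keeps it out of the trough windows. The sponsor did write such a limit elsewhere: the on-treatment FEV1 analysis stops at last dose + 14 days (SAP 2.4.4.1.2), and the on-treatment efficacy windows accept only treatment-epoch measurements (SAP 2.5.4). Concentrations have no equivalent.

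Systemic exposure is a stated secondary objective, and two regimens are studied side by side. The trough tables by dose would understate exposure on treatment. The concentration-by-visit plots by anti-drug-antibody class (SAP 2.4.6.1.2) draw on the same samples, so a low value caused by stopping could be misread as an antibody effect.

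**Working it through.** The plan states no trough level and no bias figure, so there is nothing of its own to reproduce. The check has four steps.

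**1. Follow one sample.** Take a patient whose last injection is at Week 12 and who keeps attending.

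- The Week 52 sample falls near Day 365, inside the Table 10 drug-concentration window of Days 309-378.
- It is 52 - 12 = 40 weeks after the last dose. The treatment epoch in SAP 2.1.4 ended 2 weeks after that dose.
- The patient is in the PK population, which needs only one evaluable result per patient.
- The injection and sampling dates are known, so the missing-date exclusion does not apply.
- The closest-to-target rule only chooses between samples in the same window.

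The value therefore enters the Week 52 trough of the assigned dose. If it is below the quantification limit of 0.078 mg/L (protocol Table 2), it enters as 0.078 / 2 = 0.039 mg/L.

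**2. Effect on each statistic.** Let p be the share of a visit's samples that are off drug and C the on-treatment geometric mean. Neither is in the documents. I assume C = 10 to 80 mg/L and p = 5% or 10%.

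- Full washout, all off-drug samples at 0.039 mg/L: ratio of geometric means = (0.039/C)^p.
- Partial washout, half at 0.039 mg/L and half at 25% of C: ratio = (0.039/C)^(p/2) x 0.25^(p/2).
- Arithmetic mean, full washout, taking C as the on-treatment mean: fall = p x (1 - 0.039/C), which is close to p.
- Median, with off-drug values below the on-treatment centre: the reported median is the on-treatment quantile at (0.5 - p)/(1 - p). For p = 5% this is 0.45/0.95 = 0.474.

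| | p = 5% | p = 10% |
|---|---|---|
| Geometric mean, full washout, C = 10 | 0.0039^0.05 = 0.758, fall 24% | fall 43% |
| Geometric mean, full washout, C = 80 | 0.0004875^0.05 = 0.683, fall 32% | fall 53% |
| Geometric mean, partial washout, C = 10 | fall 16% | fall 29% |
| Geometric mean, partial washout, C = 80 | fall 20% | fall 36% |
| Arithmetic mean, full washout | fall about 5% | fall about 10% |
| Median, log-SD 0.7 (range for log-SD 0.5-1.0) | fall about 5% (3-6%) | fall about 9% (7-13%) |

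**3. Which visits are affected.** Week 2 is essentially untouched: chart 1.3 starts at Week 4, and a Week 2 sample falls about 14 days after the first dose whether or not dosing goes on. Week 4 is the first visit at which a stopped patient can be beyond one dosing interval. Soon after stopping, concentrations are still measurable, so each affected sample pulls harder as time off drug grows.

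**4. Follow-up visits.** Completers take their last dose at Week 50, so at Week 64 they are 64 - 50 = 14 weeks past it. A patient who received only the loading dose can be up to 64 - 0 = 64 weeks past it. Weeks 56 and 60 are not mixed, because early stoppers do not have those visits.

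**The case against.** The strongest reply is that little depends on these tables. They are descriptive, no concentration comparison appears in the testing hierarchy (SAP Table 6), and the median, minimum and maximum are reported beside the geometric mean. Protocol 11.4.4.1 also foresees population PK modelling if warranted, described in a separate document, and SAP 2.4.6.1.2 provides individual PK plots by antibody status. All of this stands and limits the consequence. It does not make a by-dose trough correct when it contains washout samples.

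The second reply concerns size. Protocol 4.2.4 reports few discontinuations in completed trials, although with dosing for up to 16 weeks rather than 52. Patients who withdraw from the study give no sample, so p is not the discontinuation rate, and recent stoppers are still measurable. This also stands. A reader might infer that the trough loses a third or a half of its value, or that the tables will show exposure falling over time or differing between doses. The documents do not support either inference: they give no trough, no share of stopped patients who keep attending, and no difference in stopping between arms.

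A reader might also reach for a tighter filter, keeping only pre-dose samples 11-17 days after the previous injection. That does not fit the protocol. There is no Week 52 dose, so a pre-dose condition would remove the Week 52 trough. Visits are anchored to the first injection with a 3-day window, so an injection 3 days off schedule and a visit 3 days off the other way give 14 - 6 = 8 to 14 + 6 = 20 days between them in compliant patients. Patients still on treatment who missed or delayed doses would be lost as well.

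**Conclusion.** The rule is wrong as written. Assigning every available concentration to the visit windows, with sampling continuing after permanent discontinuation, biases the by-dose trough summaries and the by-visit plots by antibody class low from about Week 4 to Week 52. At Week 64 it mixes very different times since last dose. The direction follows from the text, but the size does not. At an assumed 5% off-drug share the geometric mean falls by about 16-32% and the median by about 5%. These figures rest on assumed troughs of 10-80 mg/L, half to all of the off-drug samples being below quantification, and a log-SD of 0.7 for the median. Only descriptive PK output, including the concentration displays by antibody class, is affected. A reader might infer that the efficacy results or the Week 56 and 60 follow-up values are compromised too; the documents support neither.

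**What to change.** In SAP 2.4.6.1.1 and 2.5.4:

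- For patients who permanently discontinue early, exclude from the Week 4-52 trough summaries and by-visit plots any sample taken after the treatment epoch (last dose + 14 days), with an explicit visit-window allowance. The protocol allows 3 days in general and 5 days after permanent discontinuation; the SAP should say which applies.
- Keep the Week 52 sample of completers, and all samples from patients still on treatment who missed or delayed doses.
- Summarise Week 64 for completers separately from early stoppers. Weeks 56 and 60 need no change.
- Report post-discontinuation samples in their own table or plot by time since last dose, so that no data are lost.

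The cost is a few sentences and one derived variable, days since last injection, from dates that 2.4.6.1.1 already requires. The downside is slightly fewer samples per visit in the trough tables.
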